#### ***Suspected hemolysis:***

Subjects fulfilling criterion A and at least 1 of criteria B will be considered to have “suspected hemolysis.”

- Criterion A
  - Drop in hemoglobin of > 1 g/dL since the time of first administration of IMP without clinical evidence of blood loss from gastrointestinal bleeding, menorrhagia, hemoptysis, major hematoma, or injury and not explained by repeated phlebotomy
- Criteria B
  - Presence of minor criteria documented since the time of first administration of IMP, consisting of:
    - DAT positive
    - Haptoglobin < lower limit of normal
    - LDH > ULN
    - Total or indirect (unconjugated) bilirubin > ULN or jaundiced
    - Hemoglobinuria or red/dark urine
    - Hemoglobinemia
    - Spherocytosis
    - Hepatosplenomegaly

If AE of hemolysis is reported, it must be graded by the investigator:

- Grade 1 – Laboratory evidence of hemolysis only (eg, DAT positive, schistocytes, decreased haptoglobin)
- Grade 2 – Clinical evidence of hemolysis and  $\geq 2$  g/dL decrease in hemoglobin
- Grade 3 – Transfusion or medical intervention indicated (eg, steroids)
- Grade 4 – Life-threatening consequences; urgent intervention indicated
- Grade 5 – Death

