### 8.1.2.3 Monitoring for Hemolysis

For determination of hemolysis, an assessment of clinical signs of hemolysis will be performed at Week 2 and Week 5 and compared to Baseline. In combination with laboratory results confirmed or suspected hemolysis cases will be defined as follows:

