#### ***Confirmed hemolysis:***

Subjects fulfilling criterion A and at least 2 of criteria B, where 1 of the minor criteria must be direct antiglobulin test (DAT) positive after infusion and within 28 days of the first IMP infusion, will be considered to have “confirmed hemolysis.” Confirmed hemolysis will be reported as an AE.

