#### IMACS 6 CSMs:

**Patient Global Activity Assessment:** The subject will assess his/her global DM disease activity at the study visit by selecting a point on a 10-cm line with “No evidence of disease activity” on the left and “Extremely active or severe disease activity” on the right. For details, see [Appendix 5](#).

**Manual Muscle Testing of 8 Muscle Groups (MMT-8):** The Evaluating Physician will assess the MMT-8. The 8 muscles to be tested are 1 axial muscle group - neck flexors; and 7 bilateral muscles - proximal: deltoid middle, biceps brachii, gluteus maximus, gluteus medius, and quadriceps; and distal: wrist extensors and ankle dorsiflexors. DM subjects with muscle weakness (classic DM) will have MMT-8 scores  $\leq$  142 points and DM subjects with little or no muscle weakness (hypo/amyopathic DM) will have MMT-8 scores  $>$  142 points. For subjects with a muscle group not able to be assessed because of a non-DM related injury or an amputation at Baseline, the Evaluating Physician will determine the appropriate muscle weakness stratum for this subject. For details, see [Appendix 6](#).

**Health Assessment Questionnaire (HAQ):** The subject will answer a series of questions which assess how DM is affecting 8 activities of daily living: dressing/grooming, arising (position changes), eating, walking, hygiene, reach, grip, and activities, eg, running errands, chores. For details, see [Appendix 7](#).

**Muscle Enzyme:** The most abnormal muscle enzyme (CK, LDH, AST, ALT, or aldolase) at Baseline will be assessed for changes during Study Period 1 and Study Period 2. If all muscle enzymes are within normal range at Baseline, the most abnormal enzyme will be determined by considering the value in relation to the ULN range. If more than one muscle enzyme has the same highest abnormality score at Baseline, the most abnormal muscle enzyme will be chosen according to the following priority list: CK, LDH, AST, ALT, aldolase. For details, see [Appendix 8](#).

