Anti-Jo-1 (anti-histidyl-tRNA synthetase) autoantibody present	3.9	3.8	Autoantibody testing in serum performed with standardised and validated test, showing positive result
Elevated serum levels of creatine kinase (CK)* or lactate dehydrogenase (LD)* or aspartate aminotransferase (ASAT/AST/SGOT)* or alanine aminotransferase (ALAT/ALT/SGPT)*	1.3	1.4	The most abnormal test values during the disease course (highest absolute level of enzyme) above the relevant upper limit of normal
Muscle biopsy features—presence of:			
Endomysial infiltration of mononuclear cells surrounding, but not invading, myofibres	1.7		Muscle biopsy reveals endomysial mononuclear cells abutting the sarcolemma of otherwise healthy, non-necrotic muscle fibres, but there is no clear invasion of the muscle fibres
Perimysial and/or perivascular infiltration of mononuclear cells	1.2		Mononuclear cells are located in the perimysium and/or located around blood vessels (in either perimysial or endomysial vessels)
Perifascicular atrophy	1.9		Muscle biopsy reveals several rows of muscle fibres, which are smaller in the perifascicular region than fibres more centrally located
Rimmed vacuoles	3.1		Rimmed vacuoles are bluish by H&E staining and reddish by modified Gomori trichrome stains

\*Serum levels above the upper limit of normal.

*To be enrolled subject must have a minimum aggregate score of 5.5 without and 6.7 with muscle biopsy*

ACR = American College of Rheumatology; ADM = amyopathic dermatomyositis, DM = dermatomyositis; EULAR = European League Against Rheumatism; IBM = inclusion body myositis, IIM = idiopathic inflammatory myopathies; IMNM = immune-mediated necrotizing myopathy; JDM = juvenile dermatomyositis; PM = polymyositis.

[figure not shown]
Source: [Lundberg et al, 2017](#).

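### In subjects whose LDH is above ULN at Baseline and stays there, the hemolysis definition meets one minor criterion in advance, so suspected hemolysis reduces to the hemoglobin fall alone

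*Protocol*

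**What the plan says.** Protocol 8.1.2.3 sets two categories. Both need criterion A, "Drop in hemoglobin of > 1 g/dL since the time of first administration of IMP", with no bleeding, injury or repeated phlebotomy to explain it.

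- Suspected: "Subjects fulfilling criterion A and at least 1 of criteria B will be considered to have" suspected hemolysis.
- Confirmed: "Subjects fulfilling criterion A and at least 2 of criteria B, where 1 of the minor criteria must be direct antiglobulin test (DAT) positive". That DAT result has to fall after infusion and within 28 days of the first infusion. Confirmed cases are to be reported as AEs.

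The eight criteria B are introduced as "Presence of minor criteria documented since the time of first administration of IMP, consisting of". They include LDH above ULN, positive DAT, haptoglobin below the lower limit of normal, and raised bilirubin. The only comparison with Baseline in the section concerns clinical signs: "an assessment of clinical signs of hemolysis will be performed at Week 2 and Week 5 and compared to Baseline".

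SAP 11.6.4 repeats the definition. It adds medical review for hemoglobinuria, hemoglobinemia and hepatosplenomegaly, but not for LDH. The results are reported as number and percentage of subjects.

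LDH has a second role in this trial. Protocol 8.1.5 states: "The most abnormal muscle enzyme (CK, LDH, AST, ALT, or aldolase) at Baseline will be assessed for changes". Protocol Appendix 2 also lists raised LDH among the enzyme findings that score towards the disease classification.

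**The concern.** A marker of the disease under study is reused as a marker of a drug risk, with no adjustment for where the subject started. LDH is not in the hemolysis laboratory panel (Protocol Table 2 notes). It is drawn only with the muscle enzymes. A subject who enters with raised LDH from muscle disease, and whose LDH stays raised, meets a criterion B at the first post-infusion muscle-enzyme sample, whatever is happening to the red cells.

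Hemolysis is one of three risks for which the protocol sets specific monitoring, beside thromboembolic events and corticosteroid effects. The count of suspected and confirmed cases is how the risk will be read. If some of those cases are a hemoglobin fall beside long-standing LDH elevation, the table is less specific than it looks, and it contains nothing that lets a reader separate them.

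**Working it through.** **Logic.** The plan gives no expected hemolysis rate, so there is no figure to reproduce. Write A for criterion A and count the criteria B that are met:

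- Suspected = A and (number of B ≥ 1).
- Confirmed = A and DAT positive and (number of B ≥ 2).

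The eight criteria B give 2^8 = 256 combinations. Without A, none is a case. With A but without a positive DAT, none is confirmed. For a subject whose LDH was high at Baseline and remains high:

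| Findings after first infusion | As written | Baseline-high LDH not counted |
|---|---|---|
| LDH high, no A | not a case | not a case |
| A + LDH high | suspected | not a case |
| A + LDH high + DAT positive | confirmed | suspected |

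For this subject the number of B is already 1. Suspected becomes A alone, and confirmed becomes A plus a positive DAT. Baseline DAT is drawn (Protocol Table 2), but the text "where 1 of the minor criteria must be direct antiglobulin test (DAT) positive after infusion and within 28 days of the first IMP infusion" does not require it to have been negative.

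**Size.** The documents give neither the share with raised Baseline LDH (q) nor the probability of meeting criterion A (pA). Assume q = 20-60%, pA = 5-20%, independence, and LDH staying high. The planned 126 subjects give 63 per arm. The expected number per arm meeting A plus the LDH criterion through Baseline-high LDH is 63 × q × pA:

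- low: 63 × 0.20 × 0.05 = 0.63
- middle: 63 × 0.40 × 0.10 = 2.52
- high: 63 × 0.60 × 0.20 = 7.56

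Some of these would also meet another criterion B and remain cases. Let r be the probability of any other B, assumed independent, with no new LDH rises. Expected suspected cases among 126 are then 126 × pA × [1 − (1 − q)(1 − r)] as written, and 126 × pA × r if Baseline-high LDH is not counted. At pA = 10%, q = 40%, r = 5%:

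- as written: 126 × 0.10 × (1 − 0.60 × 0.95) = 126 × 0.10 × 0.43 = 5.4
- Baseline-high LDH not counted: 126 × 0.10 × 0.05 = 0.6

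With pA held at 10%, and q over 20-60% and r over 5-15%, the ranges are 3.0-8.3 and 0.6-1.9.

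**Effect on the comparison.** The middle case adds 2.52/63 = 4% to each arm. Suppose true rates of 5% on IgPro20 and 0% on placebo. The table would show 1 − 0.95 × 0.96 = 8.8% against 4.0%. The difference is 4.8 points instead of 5.0, but roughly half the IgPro20 cases are no longer hemolysis.

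**The case against.** The strongest reply is that suspected hemolysis is meant to be a sensitive category, that the same rule applies to both blinded arms, and that the analysis is descriptive. The illustration supports this in part: the risk difference hardly moves, and no test or ratio is planned. SAP 11.5 also summarizes LDH by visit and flags out-of-range values in listings, so a determined reader could trace Baseline LDH case by case. That leaves the table itself without the information.

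The link from disease to LDH should not be overstated either. Protocol 3.3.1 notes that muscle enzymes can be normal in active DM, subjects can enter on skin activity without weakness, and the Appendix 2 item covers four enzymes over the disease course. The opportunity is also limited. Hemolysis monitoring is at Weeks 2 and 5, and of those two visits muscle enzymes are drawn only at Week 5. However, neither document states an end date for the suspected category.

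A reader might infer three stronger things, which the documents do not support:

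- **That active dermatomyositis alone is classified as hemolysis.** Criterion A is always required, and confirmed cases also need a positive DAT.
- **That the rule leads to IMP discontinuation.** Protocol 4.3.1 ties discontinuation to Grade 3 hemolysis, not to meeting the case definition. Laboratory evidence only is Grade 1. A suspected case carries no automatic AE.
- **That the rule biases towards hiding a drug effect.** This would need IgPro20 to lower LDH differentially, largely by Week 5. The protocol places comparable exposure to IVIG at 8 to 10 weeks and bars rescue before Week 9 to allow for steady state. The idea is speculative.

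The exemption in Protocol 9.1.1 for values already abnormal at Screening limits AE reporting of isolated laboratory findings. It does not enter the case definition.

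**Conclusion.** The point holds as a modest loss of specificity. For subjects with LDH above ULN at Baseline and afterwards, one criterion B is met before treatment has done anything, and neither the protocol nor the SAP corrects for it. The wording and its logical consequence are certain; the size is not. The range of 0.6 to 7.6 subjects per arm rests entirely on assumed values of q and pA and on their independence, and it includes some subjects who would be cases by another criterion anyway. The loss applies to both arms, and nothing in the documents shows that it favors either one. It justifies an inexpensive addition to the analysis. It does not justify rewriting the protocol's case definition, which is a clinical rule.

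**What to change.** In SAP 11.6.4, keep the current definition for the main table and leave AE reporting as it is. Add a second tabulation in which LDH, DAT, haptoglobin and bilirubin count as criteria B only if they were absent at Baseline. Show suspected and confirmed cases by arm and by Baseline LDH status (≤ ULN, > ULN). Leave the other criteria B as they stand; the blood smear, for example, is analyzed only at Weeks 2 and 5 and has no Baseline value. Use the Baseline rule of SAP 8.2.5, and state that a criterion with no pre-infusion value is counted as in the main table.

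The cost is one extra table and a Baseline comparison in programming. All four values are already drawn before the first infusion. The downside is that, in the second table only, a genuine further LDH rise in a subject with high Baseline LDH is not counted; it stays in the main table. An LDH rise from a muscle flare in a subject with normal Baseline LDH would still count in both.

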### 8.1.3 ANA, MSA, and MAA Assessments

Additional blood samples for presence of ANA, MSA, and MAA will be collected at Screening, Week 25, and Week 53 (Table 11).

The following MSA will be analyzed: anti-Jo-1, anti-PL-7, anti-PL-12, anti-EJ, anti-OJ, anti-SRP, anti-Mi-2, anti-p155/140, anti-TIF-1 $\gamma$ , anti-MDA5, anti-NXP-2, anti-HMGCR, anti-SAE-1Ab.

The following MAA will be analyzed: anti-PM/Scl, anti-Ro-SSA, anti-Ku, anti-U1 RNP, anti-U3 RNP.

The samples for ANA, MSA, and MAA will be analyzed by the central laboratory (ANA) and a specialized reference laboratory (MSA and MAA).

**Table 11 Clinical Procedures: ANA, MSA, and MAA Assessments**

Procedure	Description
ANA, MSA, and MAA assessments	Blood samples will be collected for ANA, MSA, and MAA assessments

ANA = antinuclear antibody; MAA = myositis-associated autoantibodies; MSA = myositis-specific autoantibodies.

### 8.1.4 Pharmacokinetic Assessments

Trough serum samples for IgG level determination will be collected at Screening and at specified study visits (Table 12).

Additional blood samples for rich PK sampling of IgG levels will be collected at Week 37 (Study Period 2). Rich PK samples will be collected from up to 10 Japanese subjects and 30 non-Japanese subjects. The Week 37, 168-hour rich PK blood sample must be drawn before start of Week 38 dose infusion. The additional samples will be collected at the times listed in [Table 14](#). Blood draws for rich PK samples may be drawn by a phlebotomist at the subject's home where available and/or allowed by local law.

The samples for serum IgG concentrations will be analyzed by the central laboratory by immunoturbidimetry. Serum IgG levels will not be disclosed to the investigative site or any blinded study personnel prior to unblinding the study. See [Schedule of Assessments for Rich Pharmacokinetic Sampling](#) for details.

**Table 12 Clinical Procedures: Pharmacokinetic Assessments**

Procedure	Description
Pharmacokinetics evaluations	Blood samples will be collected for IgG level determination

IgG = immunoglobulin G.

### 8.1.5 Efficacy Assessments

Efficacy assessments are to be performed by the Evaluating Physician and the subject at time points as detailed in the [Schedule of Assessments](#). The time windows for each type of assessment are detailed in [Section 8.5.1](#).

#### IMACS 6 CSMs:

**Patient Global Activity Assessment:** The subject will assess his/her global DM disease activity at the study visit by selecting a point on a 10-cm line with “No evidence of disease activity” on the left and “Extremely active or severe disease activity” on the right. For details, see [Appendix 5](#).

**Manual Muscle Testing of 8 Muscle Groups (MMT-8):** The Evaluating Physician will assess the MMT-8. The 8 muscles to be tested are 1 axial muscle group - neck flexors; and 7 bilateral muscles - proximal: deltoid middle, biceps brachii, gluteus maximus, gluteus medius, and quadriceps; and distal: wrist extensors and ankle dorsiflexors. DM subjects with muscle weakness (classic DM) will have MMT-8 scores  $\leq$  142 points and DM subjects with little or no muscle weakness (hypo/amyopathic DM) will have MMT-8 scores  $>$  142 points. For subjects with a muscle group not able to be assessed because of a non-DM related injury or an amputation at Baseline, the Evaluating Physician will determine the appropriate muscle weakness stratum for this subject. For details, see [Appendix 6](#).

**Health Assessment Questionnaire (HAQ):** The subject will answer a series of questions which assess how DM is affecting 8 activities of daily living: dressing/grooming, arising (position changes), eating, walking, hygiene, reach, grip, and activities, eg, running errands, chores. For details, see [Appendix 7](#).

**Muscle Enzyme:** The most abnormal muscle enzyme (CK, LDH, AST, ALT, or aldolase) at Baseline will be assessed for changes during Study Period 1 and Study Period 2. If all muscle enzymes are within normal range at Baseline, the most abnormal enzyme will be determined by considering the value in relation to the ULN range. If more than one muscle enzyme has the same highest abnormality score at Baseline, the most abnormal muscle enzyme will be chosen according to the following priority list: CK, LDH, AST, ALT, aldolase. For details, see [Appendix 8](#).

#### **Myositis Disease Activity Assessment Tool (MDAAT) for Physician Global Disease**

**Activity and Extramuscular Global Assessment:** The MDAAT is a combined tool which will capture the Evaluating Physician's assessment of disease activity of various organ systems using a 0 to 4 point scale as well as a VAS for each disease activity component. There are 7 extramuscular disease activity components (Constitutional, Cutaneous, Skeletal, Gastrointestinal, Pulmonary, Cardiovascular, Other [specify]) and a muscle disease activity component, each with an accompanying VAS. Additionally, an **Extramuscular Global Assessment VAS** and a **Physician Global Disease Activity VAS** will be assessed.

**Extramuscular Global Assessment and Physician Global Disease Activity** components are the 2 CSMs used for TIS and DOW calculations. In Study Period 3, only the Physician Global Disease Activity VAS will be collected. For details, see [Appendix 4](#).

## Other Measures:

**Cutaneous Dermatomyositis Disease Area and Severity Index (CDASI):** The Evaluating Physician will assess 4 disease areas (Extent [anatomical locations], Gottron's Hands, Periungual, and Alopecia) for activity and damage and provide a total score for each. For details, see [Appendix 9](#).

**Timed Up and Go:** The Evaluating Physician will measure how quickly the subject can rise from a sitting position, walk 3 meters, and return to same sitting position in Study Period 1 and Study Period 2. For details, see [Appendix 11](#).

### 8.1.6 Other Assessments

#### 8.1.6.1 Disease Specific

**Physician Global Damage Assessment:** At Screening only, the Treating Physician will rate the global (overall) assessment of current DM disease damage by using a 5-point Likert scale (0 to 4). This global assessment is to be performed using all information available to the Treating Physician at Screening, including the subject's appearance, history, physical examination, diagnostic laboratory testing, and the resultant medical therapy. For details, see [Appendix 3](#).

#### 8.1.6.2 Non-disease Specific

**5-D Itch (Pruritus) Score:** Subjects will assess 5 dimensions of itch history in Study Period 1 and Study Period 2: Duration, Degree (intensity), Direction (better or worse from previous month), Disability of 4 activities of daily living, and Distribution (location[s] on body). For details, see [Appendix 10](#).

**EuroQoL 5-Dimension Questionnaire (EQ-5D-5L):** The subject will select which best describes his own health state at the study visit in the following 5 dimensions: Mobility, Self-care, Usual Activities, Pain/discomfort, and Anxiety/depression. The subject will also select a point on a scale drawn like a thermometer to indicate how good or bad the health state is, with best state as "100" and worst state as "0." For details, see [Appendix 12](#).

**Work Productivity and Activity Impairment Questionnaire: General Health (WPAI-GH):** The subject will answer questions about the effect of his/her health on the ability to work or perform regular activities in Study Period 1 and Study Period 2. General health is defined as any symptoms relating to physical or emotional well-being. For details, see [Appendix 13](#).

**Abbreviated Treatment Satisfaction Questionnaire for Medication (TSQM-9):** The TSQM-9 is a 9-item general instrument that measures the major dimensions of satisfaction with a medication [Bharmal et al, 2009]. Scores on the TSQM-9 range from 0 (indicating poor satisfaction) to 100 (indicating perfect satisfaction). This instrument usually requires less than 5 minutes for subject completion and was developed to be used with any medication and across cultural and different language settings. Scores on the Effectiveness (3 items), Convenience (3 items), and Global Satisfaction (3 items) scales will be assessed in a cross-sectional manner in Study Period 1 and Study Period 2. For details, see [Appendix 14](#).

### 8.1.6.3 Exploratory Biomarkers

Blood samples will be collected and stored to assess exploratory biomarkers in DM for a separate, future study ([Table 13](#)). These exploratory assessments may include but will not be limited to the following: chemokines, cytokines, complement, and protein expressions, DNA, RNA, and messenger RNA. Sample collection for exploratory evaluation of biomarkers will be clearly mentioned in the ICF for this study. Sample collection for DNA testing is optional for all subjects and will require a separate consent. These potential DM biomarkers may allow for better understanding of prognosis, disease course, and correlation to treatment in DM subjects and, therefore, might allow for individualized treatment. The exploratory nature of these analyses precludes the use of the results to predict future risk or to inform health care. None of the 59 genes of potential high medical importance which appear on the American College of Medical Genetics list of published recommendations for reporting of incidental findings will be examined. Therefore, neither the investigator nor the subject will be informed of these results (DNA, RNA, or serum proteins).

In order to understand how the biomarker results might inform on these aspects of DM, they will need to be correlated with the subject's treatment in the study, gender, ethnicity, age, hematology, serum chemistry, serum IgG, efficacy and quality of life assessments. Assays will be performed in-house at CSL laboratories and by external service providers. The CSL laboratory is located at [name]. DNA samples require anonymization by the central laboratory before transfer to CSL Australia for analysis at the end of the study. All biomarker samples will be retained for a maximum of 10 years.

